The primary measurements that are anticipated to be performed on the plasma obtained from these collections will include: 25D, 1,25D, vitamin D-binding protein, heme oxygenase-1, interleukin-6, interleukin-10, thrombomodulin, parathyroid hormone, fibroblast growth factor-23, and cystatin C.

Urine

We will collect 30mL of urine at each of the above time points. In the majority of cases, urine will be collected from foley catheters placed for routine clinical care of ICU patients. Foley catheters will not be placed for research purposes. If a patient does not have a foley catheter in place for routine clinical care, urine will be collected using a bed pan, commode, or direct urination into a specimen cup. Anticipated tests that will be performed on the urine samples include neutrophil gelatinase-associated lipocalin (NGAL), interleukin 18, and kidney injury molecule-1 (KIM-1).

B. Drugs to be used

We will administer calcifediol, calcitriol, or placebo. The dosing regimens are provided in **Figure 2**. The rationale for these agents, justification of dosing regimens, and safety data are provided in sections 1C-F. Patients assigned to the placebo arm will receive medium chain triglyceride (MCT) oil, which has an identical appearance, color, consistency, and odor as calcifediol and calcitriol, both of which are also compounded in MCT oil.

Double-dummy design

Although calcifediol, calcitriol, and placebo will be identical to each other in appearance, the volumes administered will differ. For example, the concentration of calcitriol is 1 µg/ml, and therefore each 4µg dose will be administered in 4 ml. In contrast, the concentration of calcifediol is 100µg/ml. Since the first dose of calcifediol is 400µg, the first dose will also be administered in 4ml, identical to the calcifediol arm. However, calcifediol will be administered at a dose of 200µg on days 1, 2, 3, and 4 (**Figure 2**), which will be in 2ml. Therefore, to maintain blinding, we will use a double-dummy approach for drug administration on days 1, 2, 3, and 4 as follows:

Calcifediol Arm	Calcitriol Arm	Placebo Arm
Calcifediol 2ml	Calcitriol 4ml	Placebo 4ml
Placebo 4ml	Placebo 2ml	Placebo 2ml

C. Devices to be used

None

D. Procedures/surgical interventions

None

E. Data to be collected

The specific data variables that will be collected are provided in section V-A.

F. Dosing modifications

All patients enrolled will have total serum calcium levels monitored on a daily basis as part of routine clinical care in the ICU. All subsequent doses of study drug will be held for any patient who develops a total serum calcium level > 10.0 mg/dl after enrollment. Additionally, if at any time during the course of the study >10% of participants in either of the active treatment arms develops hypercalcemia, defined as per the BWH hospital laboratory as a total serum calcium level > 10.7 mg/dl, the dosing regimen for future participants assigned to that arm will be reduced by 25%. For the calcifediol arm, this 25% dose reduction would result in a new dosing regimen of 300 µg on day 0 and 150 µg on days 1, 2, 3, and 4. For the calcitriol arm, this 25% dose reduction would result in a new dosing regimen of 3 µg daily for 5 days. Unblinded safety data on hypercalcemia will be evaluated by the data and safety monitoring board (DSMB).

G. Adaptive Trial Design

After enrollment of the first 18 patients (6 patients in each of the three arms), we will stop enrollment to measure plasma 25D levels in the patients who received calcifediol to ensure that mean plasma 25D levels on days 1, 2, 3, 4, and 5 are > 50 ng/ml. If mean plasma 25D levels on days 1, 2, 3, 4, and 5 are < 50 ng/ml and the mean increase in serum total calcium levels from day 0 to day 5 is < 0.5 mg/dl, we will increase the dosing regimen for the calcifediol arm for the remaining study participants as follows:

Mean plasma 25D level on days 1 through 5	Calcifediol dose adjustment for remaining participants
40-50 ng/ml	500 µg on day 0 and 250 µg on days 1, 2, 3, and 4
<40 ng/ml	600 µg on day 0 and 300 µg on days 1, 2, 3, and 4

VI. BIOSTATISTICAL ANALYSIS

A. Specific data variables being collected for the study

The specific data variables that will be collected are provided in section V-A.

B. Study end points

Primary end point. The primary end point is a composite of renal injury, RRT, and death. Renal injury will be assessed by time-averaged (area under the curve [AUC]) levels of daily SCr for the first 7 days following enrollment. This end point has been used in previous clinical trials conducted in AKI,⁸⁹ and these measurements will be obtained through routine clinical testing. To account for missing data, we will standardize the AUC of daily SCr levels relative to the number of days in which SCr data are available. RRT and death are important confounders of SCr levels, as well as important end points by themselves, and will therefore be considered along with the AUC of SCr levels as part of the primary composite end point. RRT will be defined as receipt of any form of dialysis within the first 7 days of enrollment. Death will be defined as all-cause mortality within the first 7 days of enrollment.

To evaluate the primary composite end point, which includes both continuous (SCr levels) and dichotomous (RRT and death) variables, we will use a rank-based procedure, as prior studies have done,⁹⁰ as follows:

- Patients who die within 7 days of enrollment will be assigned the highest (worst) rank, with no difference in rank assigned to patients who die at different times within the first 7 days.
- Patients who survive >7 days but who require RRT within 7 days of enrollment will be assigned the second highest rank.
- All other patients will be assigned a rank based on the AUC of their SCr, as described above.

Secondary end points. Secondary end points will include new or worsening AKI (defined by KDIGO guidelines);⁹¹ kidney function on hospital discharge (assessed by SCr); hospital- and ICU length of stay; and hospital-, ICU-, and 28-day mortality. We will also evaluate the AUC of urinary injury biomarkers, including KIM-1, NGAL, and IL-18, during the first 5 days using a similar global rank score strategy as described above. Finally, we will evaluate organ-failure free days (assessed by daily SOFA scores) during the first 7 days following enrollment. For the cardiovascular component of the SOFA score, we will use a modified scoring system that has improved accuracy in predicting outcomes,⁹² and for the renal component we will assign a score of “4” (the highest score) to any participant who requires RRT.

C. Statistical methods

To evaluate the primary end point, we will compare the ranks between treatment groups versus the placebo group with the use of the Wilcoxon Rank Sum test. To evaluate secondary end points, we will compare means and medians between each of the active treatment groups versus the placebo group using parametric (e.g., t-test) and non-parametric (e.g., Wilcoxon Rank Sum) tests, as appropriate. To account for two active treatment groups, we will consider p values <0.025 to be significant for the primary end point. For secondary end points, all of which will be considered exploratory, we will consider p values <0.05 to be significant.

D. Power analysis

150 participants (N=50 per group) will provide >80% power to detect a 0.62 standard deviation difference in the global rank score in each of the active treatment groups vs. placebo, with a two-sided α of 2.5%.

VII. RISKS AND DISCOMFORTS

A. Complications of surgical and non-surgical procedures

Not applicable

B. Drug side effects and toxicities

The only known toxicity of vitamin D metabolites, including calcifediol and calcitriol, is hypercalcemia.^{81 82} Despite an excellent safety profile, transient hypercalcemia has been reported with calcitriol and, to a much lesser extent, with calcifediol. The risks of hypercalcemia in the current study are low, since the planned doses of calcifediol and calcitriol are lower than doses that have been used safely in prior studies in humans (discussed in detail in sections 1E and 1F). Additionally, the following precautions will further minimize risk to patients:

1) Limiting our study to patients with serum total calcium levels ≤ 9.0 mg/dl. Most prior clinical studies of calcifediol and calcitriol (discussed in sections 1E and 1F) were conducted in patients who were generally normocalcemic on enrollment. In contrast, most ICU patients have serum calcium levels in the low-normal range, and many patients (55.2% in one study)⁹³ are frankly hypocalcemic on arrival to the ICU. In the current study, we will exclude patients with serum total calcium levels > 9.0 mg/dl on enrollment (**Table 2**). By limiting enrollment to patients with serum total calcium levels ≤ 9.0 mg/dl, a substantial barrier exists for serum calcium levels to rise into the hypercalcemic range (>10.7 mg/dl) and an even larger barrier for clinically relevant hypercalcemia (>11.5 mg/dl).

2) Limited number of doses of study drug. In most prior clinical studies, calcifediol and calcitriol were administered on a regular (daily) basis for weeks to months. The current study will administer a total of only 5 doses of calcifediol or calcitriol drug over 5 days.

3) Close monitoring of total serum calcium levels. All patients enrolled will have total serum calcium levels monitored on a daily basis. Subsequent doses of study drug will be held in any patient with a serum calcium > 10.0 mg/dl.

4) Exclusion of patients with primary parathyroid disease or granulomatous disease. These conditions may be associated with upregulation of 1- α hydroxylase, which could increase the conversion of 25D to 1,25D and increase the risk of developing hypercalcemia. Additionally, we will exclude patients with symptomatic nephrolithiasis in the preceding 3 months, and those receiving oral calcium supplementation (**Table 2**).

5) Exclusion of patients receiving cytochrome P450 inhibitors. We will exclude patients receiving any of the following medications, since these drugs may inhibit enzymes involved in vitamin D metabolism and therefore could increase the risk of hypercalcemia: ketoconazole, atazanavir, clarithromycin, indinavir, itraconazole, nefazodone, nelfinavir, ritonavir, saquinavir, telithromycin, or voriconazole (**Table 2**).

6) Highly monitored setting. Patients will be in the highly-monitored setting of an ICU at a tertiary care academic hospital. Accordingly, if hypercalcemia or other adverse events occur they are likely to be appreciated immediately and appropriate resources will be readily available.

7) Pre-specified dose modification. As described in section V-F, if at any time during the course of the study $>10\%$ of participants in either of the active treatment arms develops hypercalcemia, defined by the BWH hospital laboratory as a total serum calcium level > 10.7 mg/dl, the dosing regimen for future participants assigned to that arm will be reduced by 25%.

8) DSMB. A DSMB will meet every 6 months to review unblinded data on all adverse events, with an emphasis on serum total calcium levels, and will submit a report to the IRB after each meeting. Additionally, data safety monitoring will be reviewed by investigators [name], and [name], on a weekly basis.

C. Confidentiality

Loss of confidential patient information is a potential risk in any clinical trial. To minimize this risk we will collect our database only on partners-protected computers; we will not include any protected health information in our primary database or in any study documents; the key linking the patient's study ID# with their name and medical record number will be kept in a separate folder on a partners-protected computer. The key linking the treatment group with the study ID will be kept on a separate password-protected computer by the BWH research pharmacy. Biological specimen tubes containing plasma and urine will be tagged with study ID#'s only and will not include any protected health information. Specimens will be stored in locked freezers at Brigham and Women's hospital.

Storing of genetic samples

Genetic samples will be stored in locked freezers at Brigham and Women's Hospital and kept for a maximum of 25 years. The samples will be labeled with a study ID only; no protected health information will be shared with collaborators outside of Partners. Genetic data will not be placed onto publicly available repositories such as the National Institutes of Health (NIH) central repository.

D. Device complications/malfunctions

Not applicable

E. Psychosocial risks

Not applicable

F. Radiation risks

Not applicable

VIII. POTENTIAL BENEFITS

A. Potential benefits to participating individuals

Individuals receiving calcifediol or calcitriol may derive benefit through the drug's actions on immune/inflammatory pathways that are directly involved in the pathogenesis of AKI. Our hypothesis that these pharmacologic agents may prevent/attenuate AKI in critically ill patients is supported by ample data from preclinical studies and preliminary data in humans (discussed in detail in section I).

B. Potential benefits to society

Potential benefits to society include elucidation of the physiology of vitamin D metabolism in critically ill patients. Moreover, this study will help answer important questions about mechanisms responsible for the association between vitamin D deficiency and adverse outcomes, including AKI, in critically ill patients. Understanding whether the immune/inflammatory response can be enhanced by calcifediol or calcitriol will inform the research community whether a larger study of either agent, powered to evaluate hard end points such as mortality, is justified.

IX. MONITORING AND QUALITY ASSURANCE

A. Independent monitoring of source data

Data collection will be performed by study investigators in a blinded fashion. The patient assignment key linking study ID# with treatment group assignment will be maintained securely by the BWH research pharmacy throughout the data collection period.

B. Safety monitoring

We have assembled a DSMB consisting of [name], a faculty member in the BWH Division of Nephrology, and [name], a faculty member in the BWH Division of Pulmonary and Critical Care Medicine. Drs. [name] and [name] both have experience providing care to critically ill patients and also have expertise in patient-oriented research, clinical trials, and biostatistics. The DSMB will meet every 6 months to review unblinded data on all adverse events, with an emphasis on serum total calcium levels, and will submit a report to the IRB after each meeting. The DSMB will be responsible for determining if the research should be altered or stopped.

Additionally, the PI ([name]) will review daily serum creatinine values for the first 7 days in real-time for each patient enrolled, and will take appropriate action as needed for any patient who develops hypercalcemia.

C. Outcomes monitoring

Not applicable. The primary end point is a biomarker, SCr, and will not be assessed until study completion.

D. Adverse event reporting

All adverse events and unanticipated problems involving risks to subjects and others will be reported to the PHRC in accordance with PHRC adverse event and unanticipated problems reporting guidelines:

http://navigator.partners.org/ClinicalResearch/Reporting_Unanticipated_Problems_including_Adverse_Events.pdf

We will report any adverse events to the PHRC within 5 working days/7 calendar days of the date the investigator first becomes aware of the problem. Other adverse events and minor protocol deviations will be reported during continuing review.

Additionally, in accordance with IND regulations, we will report all adverse events to the FDA in an IND safety report as soon as possible, but no later than 15 calendar days after the primary investigator ([name]) becomes aware of the safety information and determines that the information qualifies for reporting:

<http://www.fda.gov/downloads/Drugs/.../Guidances/UCM227351.pdf>

X. REFERENCES

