- i) court appointed guardian with specific authority to consent to participation in research or authority to make health care decisions for a class of diagnostic and therapeutic decisions inclusive of the proposed research;
- ii) health care proxy/person with durable power of attorney with specific authority for making health care decisions inclusive of the proposed research; or
- iii) spouse, adult child, or other close family member who knows the subject well and has been involved in their care.

For patients deemed to lack decisional capacity who are enrolled by surrogate consent, assent of subjects will be required for participation in the research unless the subject is incapable of providing assent due to his/her medical condition (such as intubation/sedation). For patients deemed to lack decisional capacity who are enrolled by surrogate consent and who subsequently regain capacity during the study, investigators will explain the study (including updating them on what has happened so far as a result of being in the study), answer any questions, and ask for written informed consent to continue to participate. Alternatively, patients will have the option of withdrawing from the study, in which case all data and biological samples collected will be destroyed.

Although written consent from surrogates in person will be obtained whenever possible as the preferred means of consent for patients who are unable to consent, for patients who do not

have a surrogate available to provide written consent in person we will ask a member of the patient's primary treatment team (e.g., doctor or nurse) to contact the surrogate (using the same PHRC preferred order described above) by telephone to inform them of the study and to ascertain their willingness to speak with one of the M.D. study investigators. The primary team member making the phone call will verify the surrogate's name and relationship to the patient, and will be provided with a printed script containing bullet points for the call (script provided as separate attachment).

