For surrogates expressing interest in hearing about the study, physician-investigator [name]., [name]., or [name]., will first describe an overview of the study and answer any questions. If the surrogate is interested in hearing more about the study, the physician-investigator will ascertain whether the surrogate has plans of coming to the hospital in the next few hours, and will therefore be available to provide in person written consent. If the surrogate states that he/she is planning on coming to the hospital in the next few hours, the physician-investigator will complete the consent process in person. If the surrogate states that he/she is not planning on coming to the hospital in the next few hours, the physician-investigator will send the consent form to the surrogate electronically, either by secure email or facsimile. After confirming that the surrogate has a copy of the consent form in front of them, the physician-investigator will summarize the required elements of informed consent, review the consent form with the surrogate, answer any additional questions, and ask for written consent. If the surrogate agrees, the physician-investigator will ask the surrogate to sign and date the consent form and to send it back electronically by secure email or facsimile. Given the time-sensitive nature of the study, the surrogate will be asked to provide written consent as soon as possible and no longer than 6 hours from the time they receive the consent form.

Non-English speaking patients will be eligible for inclusion. We will use official Partners interpreters and the PHRC approved 'short form' consent document in the native language of the patient and/or their surrogate.

Using a checklist, we will document the following items of the informed consent process for each patient:

- If consent was from subject or surrogate
- If surrogate, in-person or on the phone
- If surrogate, relationship to subject
- If surrogate, could subject assent, and if not, why not?
- Was an interpreter required and short form used?
- If subject regains capacity to consent a later time; if so, document whether the subject provides written consent to continue to participate or not
- Copy of consent form provided to subject or surrogate/
- Copy of consent form uploaded into Epic?
- Research study associated to the patient in Epic?

C. Treatment assignment and randomization

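### Destroying all data when a surrogate-enrolled patient regains capacity and withdraws can remove dosed patients from the cumulative hypercalcemia count and the final safety tables; a de-identified log per arm would prevent this

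*Combined protocol and SAP*

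**What the plan says.** Section IV.B covers patients who lack capacity, are enrolled by a surrogate and regain capacity during the study. They are asked for their own consent to continue. Otherwise "patients will have the option of withdrawing from the study, in which case all data and biological samples collected will be destroyed". The checklist at the end of IV.B has staff "document whether the subject provides written consent to continue to participate or not", but it holds no outcome or safety data.

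Other sections need the data that this rule removes:

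- Section V.F, repeated in VII.B item 7, reduces dosing for future participants in an arm "if at any time during the course of the study >10% of participants in either of the active treatment arms develops hypercalcemia".
- Section VII.B item 8 says that "A DSMB will meet every 6 months to review unblinded data on all adverse events". Section IX.B repeats this, with emphasis on serum calcium.
- Section IX.D requires adverse events to be reported to the Partners Human Research Committee (PHRC).
- Section VI.B ranks every patient. For death, "Patients who die within 7 days of enrollment will be assigned the highest (worst) rank". The only missing-data rule is that "we will standardize the AUC of daily SCr levels relative to the number of days in which SCr data are available".
- Section VI.D states that "150 participants (N=50 per group) will provide >80% power to detect a 0.62 standard deviation difference in the global rank score", at a two-sided α of 2.5%. It makes no allowance for withdrawal.

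**The concern.** The destruction rule has no exception, and no other section says what survives it. A patient may have taken study drug, become hypercalcemic, regained capacity and declined to continue. Read literally, the rule then removes that patient's calcium values and adverse events from the study data. The hypercalcemia rule is a running proportion over the whole study, so it needs every dosed patient. The plan does not say whether a deleted patient leaves the numerator, the denominator, both or neither. Dosing lasts five days and the monitoring board meets every six months, so the whole sequence can fall between two meetings.

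The rule also removes randomised patients from the primary analysis. It reaches only those who are alive with capacity when they withdraw. The AUC rule averages over the days with data and cannot rank a patient with none.

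At stake are the completeness of the safety record in dosed patients and, to a small extent, power. Study data cannot be restored after destruction.

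**Working it through.** **1. The plan's power figure.** Inputs from VI.D: 50 per arm, 0.62 SD, two-sided α 0.025. By the normal approximation, power = Φ(0.62 × √(50/2) − 2.241) = Φ(3.100 − 2.241) = Φ(0.859) = 80.5%. The stated figure of more than 80% reproduces, but only with all 50 per arm analysed.

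**2. Power after removal unrelated to arm.** The documents give no withdrawal rate, so 2%, 5% and 10% are assumptions. The same formula gives:

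| Share of each arm lost | n per arm | Power | Loss (points) |
|---|---|---|---|
| 0 | 50 | 80.5% | – |
| 2% | 49 | 79.6% | 0.9 |
| 5% | 47.5 | 78.2% | 2.2 |
| 10% | 45 | 75.8% | 4.7 |

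A simulation of the ranked end point used the Wilcoxon test, a 0.62 SD shift and 20,000 trials per case. It assumed that the worst 16% of the placebo distribution die and the next 6% receive RRT, with day-7 survivors removed at random. Power was 77% with no removal and about 76%, 75% and 73% at the three rates. With no true effect, rejection stayed at 2.3% to 2.6% against a nominal 2.5%, and the probability that an active patient ranks worse than a placebo patient was 0.500. The gap between 77% and the plan's 80% comes from ties and the rank test, not from the destruction rule.

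**3. Chance that a hypercalcemia case is deleted.** Let h be the hypercalcemia rate and q the share of patients deleted, both assumed and independent. For an arm of 50, the chance of at least one deleted case is 1 − (1 − hq)^50.

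| h | q = 2% | q = 5% | q = 10% |
|---|---|---|---|
| 2% | 2.0% | 4.9% | 9.5% |
| 5% | 4.9% | 11.8% | 22.2% |
| 10% | 9.5% | 22.2% | 39.5% |

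**4. Chance that the 10% result changes.** The plan fixes no schedule for the count. Looks after 12, 25, 37 and 50 patients in an arm are assumed, with deletion before each count (400,000 simulated arms per case). Ranges run over q = 2% to 10%.

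| h | Met becomes not met | Not met becomes met |
|---|---|---|
| 2% | 0.1–0.5% | 0.1–1.6% |
| 5% | 0.7–3.0% | 1.0–3.4% |
| 10% | 1.0–5.2% | 2.7–4.2% |

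The direction depends on who is deleted. Deleting a case turns 4/31 = 12.9% into 3/30 = 10.0%, which no longer exceeds 10%. Deleting a patient without hypercalcemia turns 5/50 = 10.0% into 5/49 = 10.2%, which now does. How the denominator is handled also matters. With one case deleted, 6/50 = 12.0% becomes 5/49 = 10.2% (still met) if the patient leaves the denominator, but 5/50 = 10.0% (not met) if the patient stays in it.

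**The case against.** The reporting duties and the destruction rule can be obeyed in sequence: an event is reported first and the study-held data are destroyed later. Calcium is measured daily in routine care, investigators review safety data weekly (VII.B item 8), and IX.D sets a limit of 5 working or 7 calendar days for reports to the PHRC. Hospital records and filed reports are not said to be destroyed. The hypercalcemia rule applies at any time in the study, so a trigger once met is not undone. All of this stands, and it confines the loss to cases deleted before they are counted, to later cumulative counts and to the final tables. It does not say how a deleted patient is counted afterwards.

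Destruction also respects people who had not themselves consented, and the consent pages are not available here. That is a fair reason not to assume that full retention would be approved. It does not stand in the way of keeping anonymous counts.

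Finally, the rule reaches only surrogate-enrolled patients who regain capacity and then decline. The documents give no rate for any of these steps, so the number could be zero.

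**Conclusion.** The point holds as a minor one that is cheap to fix. A stated rule removes safety data that other sections rely on, and nothing reconciles them. The loss of at least one hypercalcemia case per arm ranges from about 2% to 40% under assumed rates of 2% to 10%. A changed threshold result is uncommon, at most about 5% in each direction under assumed looks.

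Three stronger readings are tempting, and the documents do not support them:

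- **That the rule biases the primary comparison.** If removal is unrelated to arm, it costs about 1 to 5 points of power and nothing else. Material bias needs removal that differs by arm and relates to rank. Nothing shows either, and the blinding ("to maintain blinding, we will use a double-dummy approach for drug administration on days 1, 2, 3, and 4") makes a difference by arm less likely. A stress case of five withdrawals in an active arm and none on placebo gives 59% to 69% power. If withdrawal is unrelated to arm, though, all five falling in the active arm has probability (1/2)^5 = 1/32.
- **That only day-7 survivors are removed while every death stays at the worst rank.** The condition is being alive with capacity at withdrawal. A patient who withdraws and then dies or needs RRT within 7 days is lost too.
- **That the rule systematically hides hypercalcemia at the threshold.** Deletions can also push the proportion above 10%, in some of the cases above more often than below it.

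**What to change.** Reconcile section IV.B with V.F, VII.B and IX.B.

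- **At minimum**, before any destruction, enter in a de-identified log the number of withdrawn-and-deleted patients per arm who were dosed, and the number of these with hypercalcemia or another adverse event. The research pharmacy, which already holds the allocation key, or the monitoring board should hold the log so that investigators stay blinded. State that these patients remain in the numerator and denominator of the V.F count and in the safety tables.
- Report the number removed per arm beside the primary result, and say in VI.B or VI.C that they are not ranked.
- **If the ethics committee agrees**, reword IV.B and the matching consent text. Allocation, outcome and safety data collected up to withdrawal would then be kept and analysed as randomised, and stored samples would still be destroyed.

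The minimum costs a wording change and a short log. Retention beyond counts needs committee agreement, which cannot be assumed. The hypercalcemia threshold and the dose step are not at issue.
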